## Statistical Methods

We will use descriptive statistics to summarize baseline characteristics of the two groups and will compare them using standardized differences. The 2-year (730 days) cumulative incidence of PJI will be reported for both groups. Hazard ratios with corresponding two-sided 95% confidence intervals (CIs) will be estimated using a Cox proportional hazards regression model. We will fit both unadjusted (crude) models and propensity adjusted models using inverse probability of treatment weighting (IPTW). For the adjusted model, propensity scores will be calculated based on age in years, female sex, completed education, household income, comedications, and ECM (all collected prior to surgery). Subsequent stratified analyses will categorize the observed PJI cases by bacterial infection type (within the first 90 days postoperatively or between 91 days and 2 years) and compare crude proportions between groups based on the absolute risk difference with 95% confidence intervals.

[figure not shown]
We present several analyses corresponding to the main results with 95% confidence intervals rather than P values, and comply with 2 Acta Orthopaedica principles for concluding whether scientifically important differences exist:

- A statistically non-significant test is not sufficient to claim "no difference." To show "no difference," a smallest clinically relevant size of the difference (it might be 0) must be defined. If all clinically relevant differences are excluded from the difference's confidence interval, a "no difference" or similarity/comparability conclusion is reasonable.
- A statistically significant test does not necessarily imply a clinically important difference. The importance of the tested null hypothesis depends on the smallest clinically relevant difference that should be defined a priori. If the difference's confidence interval excludes all clinically irrelevant differences, a conclusion concerning the existence of a clinically important difference is reasonable.

To evaluate imprecision in the estimated treatment effect, a clinically important difference must first be defined. Based on an expected 2-year incidence of PJI of about 1%, a 50% increase in risk would be considered clinically relevant. In a time-to-event analysis, this corresponds to a hazard ratio of 1.5. Accordingly, non-inferiority—or absence of a clinically meaningful increase in risk—will be established if the upper bound of the 95% confidence interval for the hazard ratio remains below 1.5. We will visualize the 2-year cumulative incidence of all outcomes for both groups using the cumulative incidence functions (CIFs).

**Handling of missing data and sensitivity analyses:** Missing data is unavoidable in epidemiological and clinical research and must be explained otherwise it could undermine the credibility and validity of the research results. Missing values, for either predictors or outcomes, occur in all types of medical research. Unless prompted to do otherwise, most statistical packages explicitly exclude individuals with any missing value on any of the data analyzed. The resulting so-called "available case" or "complete case" analysis is the most common "default approach" to handle missing data, although it is rarely justified. Subjects with missing weight or height will be excluded from the analysis. Missingness of data on some of the covariates used for adjusting will be ignored but the subjects will not be excluded. Patients who will be lost during the follow up period (e.g., due to death or migration) are expected to be extremely few and no systematic difference is expected to be seen.

Therefore, this missingness of outcome data will be assumed "Missing completely at random" (MCAR), as there is no evidence to suggest systematic differences between the missing values and the observed values and will be ignored. For the purpose of sensitivity, we will potentially re-do the main analysis where missing outcome data is replaced twice, using best-case imputation ( $y=0$ ; no PJI) and worst-case imputation ( $y=1$ , PJI yes).

[figure not shown]
**Figure 1 (Mockup):** study flow chart

**Table 1 (Mockup).** Baseline characteristics at time of total knee arthroplasty

|  | Obese | Non-Obese | Std. Diff |
|--|-------|-----------|-----------|
| Age, years                                 |       |           |           |
| Female Sex, no. (%)                        |       |           |           |
| BMI, kg/m                      |       |           |           |
| Highest completed Education:               |       |           |           |
| <11 years, no. (%)                         |       |           |           |
| 11 to 15 years, no. (%)                    |       |           |           |
| >15 years, no. (%)                         |       |           |           |
| Household income:                          |       |           |           |
| Lowest (1 st quantile), no. (%) |       |           |           |
| Low (2 nd quantile), no. (%)    |       |           |           |
| Medium (3 rd quantile), no. (%) |       |           |           |
| High (4 th quantile), no. (%)   |       |           |           |
| Comedications:                             |       |           |           |
| Antithrombotics, no. (%)                   |       |           |           |
| Antibiotics, no. (%)                       |       |           |           |
| Glucose-Lowering, no. (%)                  |       |           |           |
| NSAIDs, no. (%)                            |       |           |           |
| Antiresorptives, no. (%)                   |       |           |           |
| ECM  |       |           |           |
| 0, no. (%)                                 |       |           |           |
| 1 to 2, no. (%)                            |       |           |           |
| ≥ 3, no. (%)                               |       |           |           |

Abbreviations: BMI: body mass index; NSAIDs: Non-Steroidal anti-inflammatory drugs; ECM: Elixhauser Comorbidity measure; Std. Diff: Standardized Difference.

**Figure 2 (Mockup):** Simulated data illustrating the cumulative incidence of A) Prosthetic joint infection (PJI); B) all-cause revision.

**Table 2 (Mockup):** Incidence for Periprosthetic joint infection (PJI) and all cause revision at 2 years in obese and non-obese patients with an unadjusted and adjusted analyses of the Hazard Ratios (HR) between the 2 groups over the full 2-year period

|                             | Obese   | Non-Obese | HR [95% CI*]  |
|-----------------------------|---------|-----------|---------------|
| Crude analyses:      |         |           |               |
| N                           | xx      | xx        |               |
| PJI, no. (%)                | xx (xx) | xx (xx)   | xx [xx to xx] |
| All cause revision, no. (%) | xx (xx) | xx (xx)   | xx [xx to xx] |
| Adjusted analyses:   |         |           |               |
| N                           | xx      | xx        |               |
| PJI, no. (%)                | xx (xx) | xx (xx)   | xx [xx to xx] |
| All cause revision, no. (%) | xx (xx) | xx (xx)   | xx [xx to xx] |

\*CI: Confidence Interval

**Table 3 (Mockup):** Microbial profiles in revisions for prosthetic joint infection (PJI) within the first 90 days and between 90 days and 2 years postoperatively.

|   | Obese   | Non-Obese | Absolute Risk Difference [95% CI*] |
|---|---------|-----------|------------------------------------|
| N                                  | xx      | xx        |                                    |
| PJI, 90 days, no. (%)              | xx (xx) | xx (xx)   | xx [xx to xx]                      |
| Staphylococcus aureus, no. (%)            | xx (xx) | xx (xx)   | xx [xx to xx]                      |
| Coagulase-negative staphylococci, no. (%) | xx (xx) | xx (xx)   | xx [xx to xx]                      |
| Other gram-positive, no. (%)              | xx (xx) | xx (xx)   | xx [xx to xx]                      |
| Gram-negative, no. (%)                    | xx (xx) | xx (xx)   | xx [xx to xx]                      |
| Anaerobes, no. (%)                        | xx (xx) | xx (xx)   | xx [xx to xx]                      |
| Fungal, no. (%)                           | xx (xx) | xx (xx)   | xx [xx to xx]                      |
| Mycoplasma, no. (%)                       | xx (xx) | xx (xx)   | xx [xx to xx]                      |
| polymicrobial, no. (%)                    | xx (xx) | xx (xx)   | xx [xx to xx]                      |
| Culture-negative, no. (%)                 | xx (xx) | xx (xx)   | xx [xx to xx]                      |
| PJ, 91 days - 2 years, no. (%)     | xx (xx) | xx (xx)   | xx [xx to xx]                      |
| Staphylococcus aureus, no. (%)            | xx (xx) | xx (xx)   | xx [xx to xx]                      |
| Coagulase-negative staphylococci, no. (%) | xx (xx) | xx (xx)   | xx [xx to xx]                      |
| Other gram-positive, no. (%)              | xx (xx) | xx (xx)   | xx [xx to xx]                      |
| Gram-negative, no. (%)                    | xx (xx) | xx (xx)   | xx [xx to xx]                      |
| Anaerobes, no. (%)                        | xx (xx) | xx (xx)   | xx [xx to xx]                      |
| Fungal, no. (%)                           | xx (xx) | xx (xx)   | xx [xx to xx]                      |
| Mycoplasma, no. (%)                       | xx (xx) | xx (xx)   | xx [xx to xx]                      |
| polymicrobial, no. (%)                    | xx (xx) | xx (xx)   | xx [xx to xx]                      |
| Culture-negative, no. (%)                 | xx (xx) | xx (xx)   | xx [xx to xx]                      |

\*The 95% confidence intervals (CI) will not be adjusted for multiplicity and should not be used in place of hypothesis testing.

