**Planned Statistical Analyses:** We will use descriptive statistics to summarize the baseline characteristics of the two groups. Hazard ratios with corresponding two-sided 95% confidence intervals (95%CIs) for experiencing the outcome will be estimated using a Cox proportional hazards regression model. We will fit both unadjusted (crude) model and a propensity score adjusted model calculated based on age, sex, highest completed education, household income, comedication, and Elixhauser Comorbidity Measure (ECM), all collected up to the day of surgery. Stratified analyses will categorize PJI cases by bacterial infection and compare crude proportions between groups based on the absolute risk difference with 95% confidence intervals.

**Ethical Considerations and Registration:** The study and its statistical analysis plan will be registered in clinicaltrials.org prior to conducting the study.

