## Objectives

The primary objective is to compare the incidence of periprosthetic joint infection (PJI) within 2 years of surgery between obese and non-obese patients undergoing primary total knee arthroplasty (TKA) for knee osteoarthritis. Subsequently examine the microbial profiles associated with PJI in these groups within the first 90 days and in the period from 91 days to 2 years following surgery. Finally we will compare the incidence of revision due to all causes within 2 years of surgery between obese and non-obese patients undergoing primary total knee arthroplasty.

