## Study design

The study is designed as a nationwide, register-based study investigating the influence of obesity on the microbial profile of PJI after TKA. The study will follow the REporting of studies Conducted using Observational Routinely-collected Data (RECORD) guidelines. We will be comparing the microbial profile of obese patients with BMI of  $30 \text{ kg/m}^2$  (exposed) with non-obese (unexposed) patients, defined as  $\text{BMI} < 30 \text{ kg/m}^2$ .

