## Variables

### Outcomes and endpoints

1. The primary outcome is revision due to prosthetic joint infection (PJI) within 2 years following TKA
2. The first secondary outcome is types of microbial profiles detected in the PJs, short term ( $\leq 90$  days) and long-term (91 days to 2 years)
3. Another secondary outcome is revision due to all causes within 2 years following TKA.

For the revision due to PJI, we will stratify the outcome looking into the proportions of the following groups of bacteria within the first 90 days and between 91 and 730 days following TKA:

- A. PJI due to *Staphylococcus aureus*.
- B. PJI due to Coagulase-negative staphylococci.
- C. PJI due to other gram-positive bacteria.
- D. PJI due to gram-negative bacteria.
- E. PJI due to anaerobic bacteria.
- F. PJI due to mycoplasmic infection.
- G. PJI due to polymicrobial infection.
- H. PJI with negative culture.

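### Organism groups and window-specific PJI totals are compared by crude risk difference only, although the study is framed around the influence of obesity on them and weighting is already planned for the hazard ratios

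*Combined protocol and SAP*

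**What the plan says.** The Statistical Methods section sets two standards. For PJI and all-cause revision it fits a crude Cox model and an IPTW-weighted one, where "propensity scores will be calculated based on age in years, female sex, completed education, household income, comedications, and ECM". For organisms, it sorts the observed PJI cases by type and window and will "compare crude proportions between groups based on the absolute risk difference with 95% confidence intervals". The Summary agrees: "Stratified analyses will categorize PJI cases by bacterial infection and compare crude proportions between groups".

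The mock tables repeat the split. Table 2 and sensitivity tables 1 and 3 (hazard ratios) each have a crude and an adjusted block. Table 3 and sensitivity tables 2 and 4 (organisms) each have one unadjusted risk-difference column. Those three tables also hold the header rows for total PJI up to 90 days and from 91 days to 2 years, so these totals are crude only as well. The footnotes warn about multiplicity and say nothing about confounding.

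On purpose, the Study design section describes the study as "investigating the influence of obesity on the microbial profile of PJI after TKA". The Objectives section puts incidence first: "The primary objective is to compare the incidence of periprosthetic joint infection (PJI) within 2 years of surgery". Outcomes and endpoints then lists organisms next: "The first secondary outcome is types of microbial profiles detected in the PJs".

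On missing covariates: "Missingness of data on some of the covariates used for adjusting will be ignored but the subjects will not be excluded". How such a patient receives a propensity score is not stated.

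**The concern.** The plan accepts that obese and non-obese patients need balancing before their PJI incidence is compared, and it collects age, sex, education, income, comedication and comorbidity for that purpose. It gives no reason for dropping the balancing when the same events are split by window or organism. If a covariate is unevenly spread between the groups and also relates to PJI risk or to the organism found, the crude difference mixes its effect with that of obesity. The Study design wording invites an explanatory reading that such a contrast cannot carry.

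The header rows show the gap most clearly. They contain the PJI events behind Table 2, divided at 90 days. Readers would have an adjusted 2-year hazard ratio but no adjusted result for either window.

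**Working it through.** The documents state no sample size, event count or organism frequency, so there is no plan figure to reproduce. The only input taken from them is the expected 2-year PJI incidence of about 1% (Statistical Methods). Everything else below is assumed, to show a range.

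**1. Confounding alone, obesity without effect.** Let one binary confounder have prevalence p1 = 15%, 20% or 30% in obese and p0 = 10% in non-obese patients, and multiply the risk by k = 1.5, 2 or 3.

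Crude risk ratio = [1 + p1(k − 1)] / [1 + p0(k − 1)]

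- Lowest: (1 + 0.15 × 0.5)/(1 + 0.10 × 0.5) = 1.075/1.05 = 1.024
- Highest: (1 + 0.30 × 2)/(1 + 0.10 × 2) = 1.6/1.2 = 1.333

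Spurious risk difference per 10,000 TKAs = 100 × share × (ratio − 1), where share is the fraction of PJIs due to the organism:

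- Share 10%, lowest ratio: 10 × 0.024 = 0.2
- Share 30%, highest ratio: 30 × 0.333 = 10
- All PJI over 2 years: 100 × 0.024 = 2.4 to 100 × 0.333 = 33. A header row holding a fraction f of these PJIs has f times that.

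**2. Against sampling error.** Assume 100 to 400 PJI cases per group, which at 1% means 10,000 to 40,000 TKAs per group. Half-width = 1.96 × √[R1(1 − R1)/N + R0(1 − R0)/N].

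| Row, highest ratio (1.333) | R1 vs R0 per 10,000 | Bias | Half-width, N = 10,000 | Half-width, N = 40,000 |
|---|---|---|---|---|
| Organism share 10% | 13.3 vs 10 | 3.3 | 9.5 | 4.7 |
| Organism share 30% | 40 vs 30 | 10 | 16.4 | 8.2 |
| Header row with f = 0.5 | 66.7 vs 50 | 16.7 | 21.1 | 10.6 |

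For single organisms the bias exceeds the half-width only at the strongest confounding, the commonest organism and the largest N. In a header row it does so more readily. The organism half-widths pool both windows; splitting them makes each row less precise relative to its bias.

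With PJI cases as denominator the picture is the same. For organism shares of 10% to 20% the bias is 0.2 to 6.7 percentage points, against half-widths of about 4 to 12 points.

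**3. What weighting would change.** Assume a confounder in 15% of patients (22.7% of obese, 9.9% of non-obese) that doubles PJI risk and doubles one organism's share of PJI from 15% to 30%. Obesity multiplies PJI risk by 1.5 and leaves the share unchanged. Baseline PJI risk is 80 per 10,000.

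Organism risk per 10,000 = 80 × h × [2c × 0.30 + (1 − c) × 0.15], with h = 1.5 (obese) or 1 (non-obese) and c the confounder prevalence.

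- Crude: 120 × 0.2523 = 30.3 vs 80 × 0.1947 = 15.6, difference 14.7
- Weighted (c = 0.15 in both groups): 120 × 0.2175 = 26.1 vs 80 × 0.2175 = 17.4, difference 8.7
- Part due to case mix: (14.7 − 8.7)/14.7, about 40%

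Dividing by total PJI risk gives the share among cases: crude 0.2523/1.2273 = 20.6% vs 0.1947/1.0993 = 17.7%, a spurious 2.8 points. Weighted, both are 0.2175/1.15 = 18.9%. This exact agreement arises because obesity and the confounder multiply PJI risk independently here. In general, cohort weights do not guarantee balance among PJI cases, since becoming a case depends on both obesity and the covariates.

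**4. Denominator.** The Statistical Methods text classifies observed PJI cases, while Table 3 has an N row and a risk difference. The two readings give different quantities. Cohort weights apply directly only when the denominator is all TKAs.

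**The case against.** The strongest reply is that crude is the right figure for the stated use. The Summary and Introduction want the organism profile in order to inform prophylaxis and empirical antibiotics in obese patients, which depends on the mix those patients actually have. The method is openly called crude, and the footnotes say the intervals do not replace hypothesis tests. This stands as a reason to keep the crude column. It does not answer the Study design wording.

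Second, the bias may be small against the noise. This stands for most single organism rows, less so for the header rows.

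Third, weighting may remove part of the pathway: the Introduction names raised blood glucose as a possible explanation of the link, and glucose-lowering drugs are in the propensity score. This is a fair limit on interpretation, but it applies equally to the adjusted model already planned for Table 2.

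Fourth, the Table 2 weights concern the BMI 30 cut and do not balance the BMI 40 contrast in sensitivity table 4. This stands and shapes the fix.

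Three stronger readings are tempting and are not supported. A reader might infer that organisms are the study's main aim; the Summary, Objectives and outcome list all rank them second. A reader might infer that the plan will report case mix as an effect of obesity; no section says Table 3 will be read causally. A reader might assume every patient already has a weight; the missing-data text leaves that open.

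**Conclusion.** The point holds as an inconsistency worth repairing. The first secondary outcome and the window-specific PJI totals have no adjusted analysis, although the plan frames the question as influence and already specifies weighting for the hazard ratios. How far this would move the results cannot be known from the documents. Under the assumed single confounder the crude risk ratio is off by 2% to 33%, and in most scenarios a single organism row could not show that above sampling error. The case for adjustment is therefore strongest in the header rows and the commoner organisms. These figures rest on assumed prevalences, risk ratios, organism shares and group sizes. Weighting would address only the covariates in the propensity score.

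**What to change.** - Keep the crude column in Table 3 and in sensitivity tables 2 and 4, and label it descriptive.
- Beside it, add an IPTW-weighted absolute risk difference with a robust or bootstrap 95% CI, for the header rows (up to 90 days; 91 days to 2 years) and for organism rows above an event count fixed before the analysis.
- State that the denominator is all TKAs in each group.
- Use the obese vs non-obese weights of Table 2 for Table 3 and sensitivity table 2. For sensitivity table 4 use the separate propensity weights that the adjusted block of sensitivity table 3 requires, estimated for whichever comparator applies (BMI below 40, or 30 to 40).
- Handle patients with missing covariates as in Table 2, and state how their score is formed. Table 2 needs this in any case.

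The cost is one column, since the adjusted hazard-ratio tables already require both sets of weights. The downside is wide intervals in sparse rows. The three tables hold 50 organism-by-window rows (18 + 16 + 16), and the event threshold would leave many of them crude only.

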## Data sources

The Danish Civil Registration System (DCRS) contains information on the CPR number, vital and migrant status, cohabiting status, and municipality of residence. The Danish Knee Arthroplasty Register (DKR) is nation-wide register that contains information on all primary knee arthroplasty procedures and revisions performed in Denmark, e.g., baseline characteristics as age, sex, BMI, at the time of TKA operation. The registry started in 1997 and the reporting to the registry became mandatory since 2006. DKR is known for high degree of coverage and completeness. The Danish Microbiology Database (MiBa) is a national database containing data from all samples received by the Danish clinical microbiology departments from both hospitals and general practices with complete coverage since 2010.

The Danish National Patient Register (DNPR) is a valuable tool for epidemiological research, providing longitudinal registration of diagnoses, treatments, and examinations derived from every hospital contact in Denmark with complete nationwide coverage since 1978. The Danish National Prescription Registry has kept information on all prescriptions for drugs dispensed by community pharmacies in Denmark since 1994 according to Anatomical Therapeutic Chemical (ATC) classification system (ATC codes). Data from the Danish National Prescription Registry does not include hospital dispensaries.

The Danish Registers on Personal Income and Transfer Payments contains more than 160 variables including salaries, entrepreneurial income, taxes, public transfer payments, capital income, private pension contributions, and pay-outs. In addition, Statistics Denmark provide more detailed registers on specific income transfers, including sickness benefit, old age pension, disability pension, and cash and unemployment benefits. The Danish Population Education Register provides information on education status on Danish population, and it carries high degree of validity and coverage.

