## Covariates

The cohort will be divided into two groups at baseline: obese, defined as  $\text{BMI} \geq 30 \text{ kg/m}^2$ , and non-obese, defined as  $\text{BMI} < 30 \text{ kg/m}^2$ . For descriptive purposes and adjusting, we will be using the following pre-TKA exposure covariates: age (years) at the time of TKA, sex (coded as female=1; male = 0), household income (at the year before KA, categorized into quartiles), highest completed education (at the year of KA, categorized into 3 categories: <11, 11 to 15, and >15 years). Comedication (at least one redeemed prescription 365 days earlier to index KA - 60 days for antibiotics): 1) Glucose-lowering due to the association between DM and surgical complications. 2) Antithrombotic medications and 3) NSAIDs because of the possible postoperative bleeding-related complications and 4) Antiresorptives due to the possible increased risk of revision. The last covariate to be included in matching and adjustment is Elixhauser Comorbidity Measure (ECM) (at the year of KA, categorized into 3: 0, 1-2 and  $\geq 3$ ), ECM is validated comorbidity scoring measure that has shown highest discriminative ability for the occurrence of all categories of postoperative adverse outcomes following orthopedic surgeries.

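### Does keeping patients with missing covariates, without naming a method, put the IPTW-adjusted hazard ratio at risk?

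*Combined protocol and SAP*

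**What the plan says.** The rule is in Statistical Methods, in the paragraph on missing data and sensitivity analyses: "Missingness of data on some of the covariates used for adjusting will be ignored but the subjects will not be excluded". The sentence before it deals with weight and height, and there the patients are removed from the analysis.

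The adjusted model is described earlier in Statistical Methods: "propensity scores will be calculated based on age in years, female sex, completed education, household income, comedications, and ECM". The scores then enter a Cox model as inverse probability weights.

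Under Covariates, education is "categorized into 3 categories: <11, 11 to 15, and >15 years" and income is split into quartiles. Neither has a level for unknown values, and the Table 1 mock-up has no row for them.

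The missing-data paragraph also describes what software does by itself: "Unless prompted to do otherwise, most statistical packages explicitly exclude individuals with any missing value on any of the data analyzed". Of the complete-case analysis that results, it says "although it is rarely justified". The only imputation it names is for the outcome: "missing outcome data is replaced twice, using best-case imputation".

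No rate of missing covariates is given anywhere. Data sources says of the education register that "it carries high degree of validity and coverage".

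**The concern.** A weight needs a propensity score, and a score needs every variable in the model. A patient with education or income blank gets neither unless something is done about the gap. Ignoring the gap and keeping the patient therefore look incompatible, and the plan does not say how to reconcile them.

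If an analyst simply ran the model, the incomplete patients would fall out of the adjusted analysis. That would be the complete-case analysis the plan itself criticises. The crude and adjusted hazard ratios in Table 2 would then rest on different patients, so the step from one to the other would mix confounding control with a change of population. The method would also be chosen after the data had been seen. The adjusted upper limit is judged against a margin of 1.5, so any avoidable looseness deserves a look.

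**Working it through.** There is no figure in the plan to reproduce: it states no missing rate, sample size or event count. All rates and counts below are assumptions.

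**Which variables can be blank.** Comedication is defined by a redeemed prescription, so no record reads as no. The lowest comorbidity level is a count of zero, so no record there can read as zero. Age and sex come from the arthroplasty and civil registers. That leaves education and income.

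**Share of patients affected.** Let m be the missing rate for each variable.
- Independent gaps: 1 − (1 − m)². For m = 1, 2, 3% this gives 1.99, 3.96, 5.91%.
- Same patients lack both: m itself, so 1, 2, 3%.

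A logistic propensity model fitted to 60,000 simulated rows, with independent gaps of 3% in each variable, left 3,563 rows (5.94%) without a score. With an explicit missing level, all 60,000 rows received one.

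**Precision if all of them were dropped.** The standard error of the log hazard ratio grows by 1/√(1 − loss).
- 1% loss: 1/√0.99 = 1.005.
- 5.91% loss: 1/√0.9409 = 1.031.

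**Upper 95% limit.** Take an observed hazard ratio of 1.2, events split equally between groups, and ignore the extra variance from weighting. The limit is 1.2 × exp(1.96 × √(4/events)).

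| Events, all patients | Limit, all patients | Limit after 5.91% loss | Shift |
|---|---|---|---|
| 200 | 1.583 | 1.597 | 0.014 |
| 400 | 1.460 | 1.469 | 0.009 |
| 600 | 1.408 | 1.415 | 0.007 |

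With 400 events, the loss is 4 events (1%) to about 24 events (5.91%). In none of the three rows does the limit cross 1.5.

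A crossing needs a full-cohort limit already very close to the margin. The limit equals 1.5 when 3.92/√events = ln(1.5/1.2) = 0.2231, which is about 309 events. After a 5.91% loss the full cohort would need 309/0.9409, about 328 events. Only between these counts would dropping change the conclusion, and there the full-cohort limit already lies between about 1.49 and 1.50.

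**Bias.** An expected-value calculation (no random draws) used 3 × 4 = 12 education-by-income cells. Obesity and infection risk both fell with education and income, baseline risk was about 0.8%, the true hazard ratio was 1.50 and the propensity score was saturated. Missingness was at random, or concentrated in low education and income, or that and also higher in obese patients. At 1 to 3% missing:
- dropping the patients gave 1.500;
- a missing level gave 1.501 to 1.503.

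The first result is expected. If missingness depends only on education, income and obesity, removing patients leaves the comparison within each cell intact, and with a common hazard ratio the weighted estimate does not move. The missing level is very slightly off because the few patients in it are not separated by their true education and income.

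**The case for a change.** The strongest case for a change is that the paragraph warns against default deletion and then gives the analyst no alternative, although the plan is to be registered before the study is conducted and one sentence would settle the matter. Nothing in the covariate coding or the mock-up tables points to a missing level. The word 'ignored' can also be read in several ways. Over four readings (drop, missing level, put in the lowest category, put in the highest), the adjusted hazard ratio in the calculation above spans 1.50 to 1.51 at 1% missing and 1.50 to 1.53 at 3%.

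It stands that the method is unnamed and that a clearer sentence would cost little. The inference that patients will be dropped does not stand. The rule is set directly against the exclusion of patients without weight or height, and it follows a passage that rejects the software default. An analyst who let the default run would be departing from the plan. The upper end of the 1.50 to 1.53 span comes from placing unknown values in an extreme category, which nothing in the documents suggests. Table 2 has separate N rows for crude and adjusted analyses, so a loss of patients would be visible to readers.

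Nor is there a better result to be had. A missing level did no better than dropping in the calculation. Multiple imputation was not calculated here, and it would need its own rule for combining imputed data with weights.

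**Conclusion.** No change is called for. The plan decides what matters, that these patients stay in, and leaves the mechanics to the analyst, who has standard ways of doing it. With education and income each blank in 1 to 3% of patients, 1 to 5.9% need handling. Even the reading the plan forbids moves the upper limit by at most 0.014 and leaves the point estimate at 1.50.

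This rests on assumed missing rates, on event counts of 200 to 600, on an equal split of events, and on missingness that depends on education, income and obesity but not on later infection beyond these. The last is reasonable because both values refer to the year of surgery or the year before. Higher rates would enlarge the affected share (5% in each variable gives 1 − 0.95² = 9.75%), but the documents' statement on education coverage points the other way. Below 1% missing the effect is negligible.
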